5.6 STUDY ENDPOINTS AND STATISTICAL PLAN

This study will evaluate two primary endpoints – effectiveness of a single use of RelieVRx in the reduction of acute postoperative pain by 20%; and overall effectiveness of RelieVRx as an opioid-sparing intervention, where opioid and non-opioid consumption is reduced by at least 20% over a 90-day postoperative period in the SOC+VR group compared to the SOC group.

Acute effectiveness will be evaluated using NPRS data collected before and after each use of RelieVRx (up to 3 times per day) over the 14-day postoperative period. NPRS is measured on a scale of 0-10, with 0 being the least amount of pain and 10 being the most. Because pain levels will vary by time of day administered and are expected to peak in the first 24-72 hours postoperatively and drop afterward, acute effectiveness will be evaluated at all stages of recovery. The expected 20% reduction after single use will be scaled relative to the pre-use pain score [e.g. users reporting a pre-VR pain level of 8 would need to report post-VR pain levels of 6.4 (8 * 80%) on average; users reporting pre-VR pain of 5 would need to report pain levels of 4 post-VR, etc.]. Each SOC+VR patient will use VR up to 44 times over the 14-day recovery period, requiring linear mixed model analysis to assess acute changes in pain scores while accounting for stage of recovery and other covariates, such as age, preoperative health status and opioid use, and postoperative complications. For interim and final endpoint analyses, pain %change scores will be calculated for each use and averaged for each patient across the 72-hour acute postoperative period, the following week, after 10 days, and overall. These averages will be evaluated using one-sample unpaired *t*-tests (or the nonparametric one-sample Wilcoxon signed-rank test, as needed for non-normal data).

Overall effectiveness will be evaluated by tracking daily opioid usage 90 days postoperatively in both SOC and SOC+VR groups. Average MMEs (Morphine Milligram Equivalents) per day will be compared using unpaired Student's *t*-test (or the nonparametric Wilcoxon rank-sum test) in interim and final endpoint analyses. In addition, changes in usage over time will be evaluated using linear mixed models (or nonlinear models, given data shape), accounting for variations in recovery time across patients and other covariates, such as other analgesic medications used postoperatively, preoperative opioid use, and dosage changes. A sub-analysis will compare usage in the 14-day acute postoperative recovery period.

The secondary endpoint of this study is a comparison of the cumulative experience of pain over the 14-day acute postoperative period between SOC and SOC+VR groups. In order to quantify pain that fluctuates over time, NPRS pain scores will be plotted for each patient over the acute postoperative period, using straight-line interpolation between measurements. This approach will allow for incorporation of all data collected (even if some patients participate more than others), and will avoid overemphasis on a single outcome measure (e.g. pain on day 14). Percent-areaunder-the-curve (VAS-%AUC) measurement will be calculated for each patient by adding the

PI Name: [name] Research Protocol: July 25, 2019 Version 1.2 (03/17/20)

areas of consecutive trapezoids defined by time on the x-axis and pain level measurements on the y-axis (e.g. 100% would indicate pain scores of 10 across the entire time period; 50% would indicate a linear reduction from 10 to 0 over the same time period). In interim and final endpoint analyses, NPRS-%AUC accumulated to date will be compared between groups using an unpaired Student's *t*-test (or nonparametric equivalent). In addition, linear mixed models will be used to compare cumulative pain between SOC and SOC+VR groups over time, as well as pain experienced in the inpatient postsurgical period and following days.

Additional outcome data will be compared between groups in preliminary analyses using chisquared tests (for categorical variables), unpaired Student's t-tests (for single-measure normal continuous data), or nonparametric equivalent (for non-normal data), as appropriate. For measures collected at multiple time points, %AUC values will be calculated per patient and compared using aforementioned tests. In final analyses, outcomes will be compared using linear mixed models, allowing for data missing at random and evaluation of covariates.

When approximately 25% of the total required sample has been collected, patient data will be summarized to verify adequate study power, and interim analyses will be conducted. In order to preserve a Type I error rate of 5% (i.e., $\alpha = 0.05$) for final analyses, interim analyses will be conducted with *p*-value threshold of 0.001, as suggested using the Hybittle-Peto method, meaning that only effects where d > 2.0 will be significant. Additional patients may be recruited as needed to ensure sufficient study power, and fewer patients may be recruited if interim analyses demonstrate highly significant effects. All statistical analyses will be performed with SAS (SAS 9.4, SAS Institute, Cary, NC), Stata (SE 14.2, StataCorp, LLC, College Station, TX), or R (R 3.5.2, The R Foundation, Vienna, Austria) statistical software, with p-values of <0.05 considered statistically significant.

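### Two primary endpoints, one of them tested in four time windows, are each judged at p<0.05 with no multiplicity rule, so 5% holds per test but not across the primary tests

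*Combined protocol and SAP*

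**What the plan says.** Section 5.6 opens with "This study will evaluate two primary endpoints". The first is a within-arm change in pain score after each use of the device. The second is a between-arm difference in opioid consumption over 90 days.

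- **Acute endpoint.** For the interim and final endpoint analyses, percentage changes are "averaged for each patient across the 72-hour acute postoperative period, the following week, after 10 days, and overall", and "These averages will be evaluated using one-sample unpaired *t*-tests" or the Wilcoxon signed-rank equivalent. The same paragraph says that the repeated uses call for a linear mixed model. It does not say which analysis decides.
- **Opioid endpoint.** Average MME per day "will be compared using unpaired Student's *t*-test (or the nonparametric Wilcoxon rank-sum test) in interim and final endpoint analyses", with mixed models in addition.
- **Thresholds.** At the interim look, at about 25% of the sample, "interim analyses will be conducted with *p*-value threshold of 0.001, as suggested using the Hybittle-Peto method". The sentence giving this threshold begins "In order to preserve a Type I error rate of 5" (per cent) and refers to the final analyses. All analyses are then to be read "with p-values of <0.05 considered statistically significant".
- **Sizing.** Section 5.6.1 gives each one-sample test, and the opioid test, the full 5%.

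No section supplies an alpha split, a testing order, a decisive acute window or a rule on whether one endpoint or both must succeed.

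**The concern.** Taken as written, the final analysis contains five primary-level tests: four acute windows and one opioid comparison. Each can be called significant at p<0.05. Nothing fixed in advance prevents whichever one succeeds from being presented as the primary result. The Hybittle-Peto step does not help, because it protects against looking twice at one test and not against having several tests.

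Section 8 says the data will go into a *de novo* submission to the FDA. A positive finding that could have come from any of five tests is weaker support for that than one from a test named beforehand.

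**Working it through.** **Inputs from the documents.** Two primary endpoints, four acute windows, final threshold 0.05, interim threshold 0.001 at about 25% of the sample (Section 5.6). Opioid mean 12.5 mg/day, SD 3, difference 2.5 mg, 25% attrition; acute endpoint 20% attrition; 80% power (Section 5.6.1). 50 per group (Section 5.2.1).

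**Assumptions.** The documents do not state sidedness; two-sided 0.05 reproduces their sample sizes. They give no correlation between windows, so a range is used. The opioid test is taken as independent of the acute tests. For the acute effect size, 20% is read as 2 points on an SD of 2.0 (d = 1.0), and 10% as d = 0.5.

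**Step 1: the plan's own figures.**
- Opioid: d = 2.5/3 = 0.833. A two-sample t-test at 0.05 and 80% power needs 24 per group; 24/0.75 = 32. The plan says 32.
- Acute, 20% effect: 10 evaluable; 10/0.80 = 12.5, rounded to 13. The plan says 13.
- Acute, 10% effect: 34 evaluable; 34/0.80 = 42.5, rounded to 43. The plan says 43.

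All three match with the whole 5% given to each test.

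**Step 2: does the interim rule hold 5% for one test?** With 0.001 at 25% information and then 0.05 at the end, total error is about 5.07%. For a single test the rule does nearly what it says.

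**Step 3: error across the primary tests, two-sided.**
- Two independent endpoints, one window each: 1 − 0.95² = 9.75% (upper bound 10%).
- Five tests, if all were independent: 1 − 0.95⁵ = 22.6% (upper bound 25%). The windows share patients, and the overall average is built from the other three, so this is a reference value only.
- Five tests, windows correlated. Simulation with 40 evaluable device patients (50 × 0.80), three equally correlated windows, an overall mean weighted 3:7:4 by days, and 60,000 replicates:

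| Window correlation | Any of four windows | Any window or opioid |
|---|---|---|
| 0 | 15.8% | 20.1% |
| 0.3 | 14.4% | 18.7% |
| 0.5 | 12.9% | 17.4% |
| 0.7 | 11.2% | 15.7% |
| 0.9 | 8.4% | 13.1% |

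**Step 4: only results favouring the device.** The benchmark per test is now 2.5%. Two endpoints with one window each give 1 − 0.975² = 4.9%. Five tests give 7.9% (correlation 0.7) to 9.5% (correlation 0.3) by simulation.

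**Step 5: what alpha 0.025 per endpoint would need.**

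| Test | Evaluable | Enrolled | Planned |
|---|---|---|---|
| Opioid, per group | 29 | 29/0.75 = 38.7, so 39 | 50 |
| Acute 20% effect | 13 | 13/0.80 = 16.3, so 17 | 50 |
| Acute 10% effect | 41 | 41/0.80 = 51.3, so 52 | 50 |

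Opioid power with 37 evaluable per group (50 × 0.75 = 37.5, rounded down) is 90% at 0.025, against 94% at 0.05. Acute power for the 10% effect with 40 evaluable is 79% at 0.025, against 87% at 0.05.

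**The case against.** The best defence is that the two endpoints answer separate questions, set out as Aims 1 and 3 in Section 4. The windows also have a stated reason: pain changes during recovery, so the effect is examined at each stage, with the overall average among them. On that view nobody intends each window as its own route to success. Part of this stands: the plan is silent on what counts as success, so five routes is an inference from that silence and not a stated rule. But the windows are assigned tests within the final endpoint analyses, and none is marked as descriptive. If both endpoints were required, the two-endpoint inflation would go. The acute endpoint on its own would still carry about 8% to 16% if any window sufficed.

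Three stronger readings are tempting, and the documents do not support them.

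- *The plan breaks a 5% level that it promises across endpoints.* The sentence about preserving 5% introduces only the interim threshold. It concerns repeated looks, where it roughly holds, and it makes no claim about several endpoints.
- *The false-claim risk is 22.6%, or even 16% to 19%.* The first needs independent windows. The second is a conventional two-sided family-wise rate that includes results against the device. The risk of a false claim of benefit is about half that, although its 2.5% benchmark is halved too.
- *Correcting this leaves every sample size adequate.* That is true for the opioid endpoint and the 20% acute effect. It is not true for the 10% acute effect that Section 5.6.1 also sizes.

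**Conclusion.** The concern holds as the absence of a multiplicity rule. This is more than missing detail, because following the text as written raises the primary-level error whenever any one test may carry the claim. The inflation is roughly twofold for two endpoints with one window each, and threefold to fourfold for five tests: about 16% to 19% against 5% two-sided, or about 8% to 10% against 2.5% in the device's favour.

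The five-test figures rest on assumed window correlations of 0.7 to 0.3, an independent opioid test, and the reading that any window suffices. At a correlation of 0.9 the two-sided figure is still 13.1%. The plan should be corrected before outcome data are examined, and the design itself need not change.

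**What to change.** 1. Name the overall 14-day average as the single acute primary test, by one stated analysis: either the one-sample test or the mixed model. Make the three sub-windows supportive.
2. Name the 90-day MME/day comparison as the single opioid primary test. State its data source as well, since Section 5.5 lists three ways of assessing medication use.
3. Either apply Holm across the two (smaller p-value against 0.025, then the other against 0.05), or state that both must reach p<0.05 for trial success.
4. Keep the interim threshold, and say that it governs repeated looks only.

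**Cost.** A few sentences in Section 5.6 and a restated power in Section 5.6.1. The planned 50 per group covers the opioid endpoint and the 20% acute effect even at 0.025. For the 10% acute effect, power at the 0.025 step is 79% with 40 evaluable, and Holm restores the 0.05 level when the opioid test succeeds. If the two tests are independent, acute power under Holm is about 0.90 × 0.87 + 0.10 × 0.79 = 86%. If both endpoints are required instead, joint power for the opioid target and the 10% acute effect is about 0.94 × 0.87 = 82%, again assuming independence. Restate that power; no extra enrolment is needed.

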4 SPECIFIC AIMS

4.1 SPECIFIC AIM 1

Among standard of care (SOC) plus RelieVRx (SOC+RelieVRx) group, compare pain scores before and after use of RelieVRx. *Hypothesis: Acute postoperative pain scores will decrease by at least 20% or 2 points on a 0-10 Numerical Pain Rating Scale (NPRS) after each use of RelieVRx*.

4.2 SPECIFIC AIM 2

Compare pain scores between the SOC group and SOC+RelieVRx group. *Hypothesis: Cumulative pain scores will be comparable among the SOC+RelieVRx group and SOC group.*

4.3 SPECIFIC AIM 3

Compare opioid use between the SOC group and SOC+RelieVRx group. *Hypothesis: Opioid consumption will be reduced by at least 20% over a 90-day postoperative period in the SOC+RelieVRx group compared to the SOC group.*

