5 STUDY DESIGN

5.1 **Description**

This is a prospective, randomized, controlled study of the appliedVR RelieVRx pain management solution in subjects undergoing Total Knee Arthroplasty (TKA).

Patients at each study site will be randomized by computer 1:1 to either the SOC (control) group or the SOC+RelieVRx (test) group. The SOC+RelieVRx group will receive education and hands-on experience with the VR headset and RelieVRx pain management solution at a routine preoperative patient education class or during the history and physical encounter visit through a predetermined script to make the patient feel comfortable using the device on their own. The goals of VR will be presented in the context of an alternate method of pain control to opioids. Subjects will be assured they will receive SOC analgesic management in addition to the headsets. The participating surgeons and anesthesiologists at Geisinger Medical Center will

PI Name: [name] Research Protocol: July 25, 2019 Version 1.2 (03/17/20)

adhere to a standardized medication regimen for anesthesia and pain relief prescriptions in order to minimize confounding between the groups due to differences in pain medication treatment plans.

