5.4.2 Approximate Duration of Study

This study will be completed in approximately two years. The end of the study is the last visit of the last subject or end of collection of data from the patient's electronic medical record (EMR).

PI Name: [name] Research Protocol: July 25, 2019 Version 1.2 (03/17/20)

5.5 **PROCEDURES**

Standard of Care: Both the SOC+RelieVRx group and the SOC group will be enrolled in the Geisinger ProvenRecovery Program[©], which includes a "My Rapid Recovery Kit" containing care instructions for mobility and nutrition, an antiseptic body wash to lessen the chances of infection, a spirometer to measure lung capacity, and immunonutrition drinks to avoid malnutrition and dehydration. Surgery through ProvenRecovery[©] is opioid avoiding and in many cases opioid free. During surgery, a patient's pain is controlled by targeting only the surgical area. Known as multi-modality pain management, this technique allows for effective pain control of just one area and eliminates additional pain sources. A combination of non-opioid medications is used, depending on the surgery, such as a local anesthesia, ibuprofen, acetaminophen, gabapentin, ketamine, and lidocaine.

Intervention: For all participants who are randomly assigned to the SOC+RelieVRx group, the RelieVRx headset will be provided by a study team member during the preoperative period, along with instructional materials. While in the hospital, use of the VR headset will be offered either in addition or as an alternative to SOC pain medication. The headset will be provided preoperatively, but patients will not be instructed to use the device until after their surgery. Patients will be instructed to use the device on the day of surgery after they are discharged from the Post Anesthesia Care Unit (PACU) to the inpatient unit, or at least 4 hours post-surgery. The device will then go with the patient upon discharge for use through the entire treatment period (i.e. 14 days). Participants will use the RelieVRx headset for 14 days postoperatively a maximum of 3 times per 24-hour period (morning, noon, and evening) for not more than 30 minutes consecutively. The patients will be instructed not to use the device while ambulating.

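### Aim 2 hypothesises comparable cumulative pain, but the plan tests and sizes NPRS-%AUC only for a difference and gives no margin or interval rule for concluding that pain is comparable

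*Combined protocol and SAP*

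**What the plan says.** - Section 4.2 (Specific Aim 2) states the hypothesis: "Cumulative pain scores will be comparable among the SOC+RelieVRx group and SOC group".
- Section 5.6 defines the matching endpoint: "The secondary endpoint of this study is a comparison of the cumulative experience of pain over the 14-day acute postoperative period". The measure is the area under the pain-time line as a percentage of its maximum; on this scale "100% would indicate pain scores of 10 across the entire time period".
- For the interim and final analyses, section 5.6 says that "NPRS-%AUC accumulated to date will be compared between groups using an unpaired" Student's t-test or its nonparametric counterpart. Linear mixed models are added. The final rule is "with p-values of <0.05 considered statistically significant".
- Section 5.6.1 (Secondary Endpoint) takes simulated group means of 0.86 and 0.79 with SD 0.1 (d = 0.7). It gives 68 evaluable patients for a significant result at 5% Type I error and 80% power, and 92 enrolled at 25% attrition. Section 5.2.1 plans about 100 patients, 50 per group.
- Section 5.6.1 also mentions the requirements of a noninferiority trial, but for opioid sparing, not pain. It gives no margin or test for it.

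**The concern.** The hypothesis and the test point in different directions. A significant t-test would contradict Aim 2 or at least fail to support it. A non-significant one would show only that no difference was detected. The plan does not say whether comparable means not worse (noninferiority) or neither better nor worse (equivalence), by how much, or on what interval.

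This matters for reading the opioid result. Section 5.5 says "While in the hospital, use of the VR headset will be offered either in addition or as an alternative to SOC pain medication", while section 5.1 says "Subjects will be assured they will receive SOC analgesic management in addition to the headsets". The two statements should be reconciled, but on either one a reader who sees lower opioid use will ask whether pain was worse. The data to answer are collected. A margin chosen after the results are known would not be credible, and section 8 plans both publication and a regulatory submission.

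**Working it through.** **Inputs.** Difference 0.07 and SD σ = 0.1 (section 5.6.1); Type I error 5%, taken as two-sided; power 80%; attrition 25%; 1:1 allocation (section 5.1); about 50 per arm enrolled (section 5.2.1). Evaluable per arm: 50 × 0.75 = 37.5, taken as 37. The margins M of 7, 6 and 5 points are illustrative assumptions, because the documents give none.

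**1. The plan's own figure.** In a two-sample t-test with d = 0.07/0.1 = 0.7, two-sided 0.05 and 80% power, the solution is 33.02 per arm, rounded up to 34, so 68 in total. With attrition, 34/0.75 = 45.3, so 46 per arm and 92 in total. Both figures reproduce exactly. A one-sided 5% test would need only 26 per arm (52). The endpoint is therefore sized as a two-sided test of difference.

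**2. How often a real difference gives p ≥ 0.05.** SE = σ√(2/n) = 0.1 × √(2/37) = 0.02325, with 72 degrees of freedom and noncentrality δ/SE.

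| True difference δ | δ/SE | P(p ≥ 0.05) |
|---|---|---|
| 3 points | 1.29 | 75% |
| 5 points | 2.15 | 44% |
| 7 points | 3.01 | 16% |

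**3. Width of the interval.** The 95% half-width is t(0.975, 72) × SE = 1.993 × 0.02325 = 0.0463, about 4.6 points. A result just short of significance against SOC+VR would have an upper limit near 2 × 4.63 = 9.3 points, beyond the 7 points the plan is sized to detect.

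**4. What a margin would require.** True difference 0, n = 37 per arm, SD 0.1. Noninferiority power is the probability that a noncentral t variable (72 df, noncentrality M/SE) exceeds 1.993. Equivalence power is the probability that the whole interval lies within ±M, integrated over the sampling distribution of the SD.

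| Margin | Noninferiority (upper limit of 95% CI) | Equivalence, 90% CI | Equivalence, 95% CI |
|---|---|---|---|
| 7 points | 84% | 82% | 69% |
| 6 points | 72% | 64% | 44% |
| 5 points | 56% | 37% | 14% |

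At 7 points, 80% power takes 92, 96 and 118 enrolled respectively.

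**5. Scale of the sizing inputs.** The sizing paragraph does not say how 0.86 and 0.79 were formed, beyond that the data were simulated. Assume straight lines from 8.50 to 6.16 and from 8.50 to 4.93. The averages are 7.33 and 6.715. Divided by 10, as section 5.6 defines the measure, they give 0.733 and 0.672, a difference of 0.0615. Divided by 8.50, they give 0.862 and 0.790, which match the plan. If the means need rescaling but the SD stays 0.1, d is about 0.615, and a test of difference needs 86 evaluable and 116 enrolled. This is conjecture: section 5.6 says pain levels "are expected to peak in the first 24-72 hours postoperatively and drop afterward", so the simulated curve may not have been a straight line.

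**The case against.** The strongest reply is that the harm is conditional. A reader might infer that the sponsor intends to treat a non-significant t-test as proof of comparability. The documents do not say so, and the percentages in step 2 measure a misreading that nobody has announced. That stands. What remains is that no other route to the Aim 2 conclusion is given either.

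A second reply is that the analysis is usable as it is, since a t-test or mixed model yields a confidence interval. This also stands: the missing item is the rule for reading the interval. The final mixed models may adjust for covariates, which could narrow the interval below the unadjusted 4.6 points; the documents give no figure for the gain.

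A third is that comparable is informal wording. It is, however, the stated hypothesis of a numbered aim, and if no claim is intended, rewording it costs one sentence.

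It is also tempting to read the noninferiority phrase in section 5.6.1 as covering pain, or the 7 points as a margin. The phrase concerns opioid sparing, and the 7 points are presented as an effect to detect.

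One caution is separate. Section 5.5 adds scores before and after each device use in the SOC+RelieVRx arm only. If these enter the area calculation they could affect the comparison, and a margin would not settle that.

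**Conclusion.** The point holds as a mismatch between hypothesis and test, with a missing margin and decision rule. It should be fixed, but it concerns the secondary endpoint only; the primary endpoint tests are unaffected.

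A reader might go further and infer that the sample size is miscalculated or that the trial is too small for Aim 2. The documents do not support either. The 68 and 92 are correct for the question they answer, and adequacy for comparability depends on a margin not yet chosen. On the assumptions used (SD 0.1 on the section 5.6 scale, 25% attrition, true difference 0, unadjusted t-test), the planned 100 gives at least 80% power at a 7-point margin for noninferiority or for equivalence on a 90% interval. It does not for equivalence on a 95% interval, nor at 6 or 5 points under any of the three rules.

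**What to change.** Choose one option and write it into sections 5.6 and 5.6.1.

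**Option A.** Base the Aim 2 conclusion on the confidence interval for the mean NPRS-%AUC difference (SOC+VR minus SOC) against a pre-stated, justified margin on the section 5.6 scale. Say whether comparable means noninferiority or equivalence and at what interval level, and give the matching power. The cost is one margin justification and a restated power, which may be low (step 4). For a secondary endpoint, restating the power is the proportionate response to any shortfall.

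**Option B.** Restate Aim 2 as a test of difference. The cost is that the trial gives up any claim that pain was comparable. The existing 68 and 92 support this option only if 0.86, 0.79 and SD 0.1 are on the section 5.6 scale, which the sponsor should confirm first.

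Under either option, state that p ≥ 0.05 will not be reported as comparability. Both are changes to protocol wording and need no new data items.

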 - Every 4 hours during patient's hospital stay
 - Daily for the remainder of the first 14 postoperative days
 - Before (within 15 minutes prior to use) and immediately after each use of their device
- Physical function will be assessed by the KOOS Jr. (Knee Osteoarthritis Outcome)
- Analgesic medication use will be assessed in three ways:
 - Reviewing inpatient use as recorded in EMR
 - Extrapolating total milligrams of morphine equivalent doses filled from PDMP database through 90-days postoperative
 - Patient self-reported consumption
- Quality of life will be assessed using the Veterans RAND 12 Health Survey (VR-12) physical component score
- PACU length of stay (LOS)
- Hospital LOS
- Time to initial ambulation
- Clinic and emergency department visits within 90-days postoperative
- Inpatient readmissions for uncontrolled pain within 90-days postoperative
- Surgical complications, such as infection or delayed healing, within 90-days postoperative

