5.6.1 Sample Size Considerations

This study has been designed with consideration for power requirements of both primary and secondary endpoint evaluations, as well as requirements for a noninferiority trial evaluating the overall effectiveness of RelieVRx as an opioid-sparing product.

Primary Endpoints

Preliminary data collected at Geisinger Medical Center (Danville, PA) between March 2017 and December 2018 from 1,052 patients who underwent total joint arthroplasty showed an average postoperative pain score of 8.50 following the procedure, and 6.16 on day 2 (SD = 2.0; change d = 1.2, or a 28% pain reduction) under SOC.

To assess the acute effectiveness endpoint of 20% average reduction in pain scores, each onesample *t*-test only requires data from 13 patients to demonstrate a significant difference from zero, assuming 20% attrition, a Type I error rate of 5% and a Type II error rate of 20% (i.e., 80%

PI Name: [name] Research Protocol: July 25, 2019 Version 1.2 (03/17/20) power). In order to observe significance of a lower threshold (e.g., a 10% reduction in pain level on average), data from **43 patients using VR** will be required, assuming 20% attrition, a Type I error of rate 5% and 80% power.

To assess the overall effectiveness for reducing opioid usage by at least 20%, this study assumes an average MME per day of 12.5mg (SD = 3) across all users, although continuous opioid users may report averages higher than 50mg/day. Observing a 20% relative reduction in opioid usage in the SOC+VR group compared to SOC (2.5mg) will require **64 patients total (32 per group)**, assuming 25% attrition, a Type I error rate of 5% and 80% power. If interim data analysis reveals unexpectedly high variability in opioid consumption, a revised power calculation based on new data may increase data collection requirements to address this question.

Secondary Endpoint

Using aforementioned preliminary data, two patients groups were created with simulated VAS-%AUC data (with day 14 VAS means of 6.16 and 4.93, SD = 2.0; or, a 20% greater reduction at day 14) corresponding to a 7% difference in VAS-%AUC (0.86 versus 0.79; SD = 0.1; difference d = 0.7). Assuming 25% attrition, the study will require **92 patients total** (**46 per group**). Data from at least 68 patients is needed to observe a statistically significant VAS-%AUC difference between SOC and SOC+VR of 7% in an unpaired *t*-test, with a Type I error rate of 5% and 80% power.

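### The supporting comparison of inpatient and later pain is split at each patient's discharge, so a between-arm difference in hospital stay would bias it even if pain is identical; the 14-day %AUC test is not affected

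*Combined protocol and SAP*

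**What the plan says.** The secondary endpoint in 5.6 is a "comparison of the cumulative experience of pain over the 14-day acute postoperative period", summarised as a percent area under the curve (%AUC) and tested between arms. The same paragraph then adds mixed models for cumulative pain over time, "as well as pain experienced in the inpatient postsurgical period and following days". It gives no hour or day at which the first phase ends, and it names no term for time since surgery in the phase comparison.

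Section 5.5 lists hospital LOS among the outcome measures. It also sets the pain sampling: "Every 4 hours during patient's hospital stay" (and whenever pain medication is requested), then "Daily for the remainder of the first 14 postoperative days".

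On the course of pain, 5.6.1 reports an "average postoperative pain score of 8.50 following the procedure, and 6.16 on day 2" under standard of care, while 5.6 says pain levels "are expected to peak in the first 24-72 hours postoperatively and drop afterward". For the acute endpoint, which concerns the RelieVRx arm only, 5.6 uses windows of fixed length, with scores "averaged for each patient across the 72-hour acute postoperative period, the following week, after 10 days, and overall".

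**The concern.** Discharge happens after randomisation, and the trial measures its timing as a possible effect of the device. A phase that ends at discharge can therefore cover different recovery times in the two arms. Pain changes quickly in these days, so moving the boundary changes the mean on each side of it without changing any patient's pain. There is also selection: the patients still in hospital on a given day are those with longer stays, possibly for different reasons in each arm.

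At stake is a named between-arm analysis that supports Aim 2 (section 4.2). A phase difference produced by LOS could be read as a treatment effect on inpatient or home pain, in either direction.

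**Working it through.** **Plan's own figures first.**
- 8.50 - 6.16 = 2.34; 2.34/2.0 = 1.17, given as d = 1.2; 2.34/8.50 = 27.5%, given as 28%.
- The planning values 0.86 and 0.79 reproduce as a straight line from 8.50 at surgery to 6.16 or 4.93 at day 14, divided by 8.5: (8.50 + 6.16)/2/8.5 = 0.862 and (8.50 + 4.93)/2/8.5 = 0.790. Section 5.6.1 therefore holds two speeds of decline: 6.16 on day 2 in the observed data, and 6.16 on day 14 in the planning simulation.
- For d = 0.7, two-sided 5% and 80% power, a t-test needs 34 per arm (68); 34/0.75 = 45.3, so 46 per arm (92). This matches the plan.

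**Inputs assumed, because the documents do not give them.** Stays of 1, 1.5 and 2 days; pain at day 14 on the observed-data curve; the starting level of 6 and peak of 8.50 in the rising scenarios. The pain curve is the same in both arms throughout.

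**Observed-data curve.** Pain at day t is 8.50 - 1.17t up to day 2 (2.34/2 = 1.17 per day), so the mean over a stay of L days is 8.50 - 0.585L.
- L = 2: 7.33. L = 1.5: 7.62. L = 1: 7.92.
- 1 versus 2 days: +0.585. 1 versus 1.5 days: +0.29.

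After discharge at day 1, the home phase gains the day 1-2 mean, (7.33 + 6.16)/2 = 6.745:
- flat at 6.16 after day 2: (6.745 + 12 × 6.16)/13 = 6.205 versus 6.16, +0.045;
- falling to 3 at day 14 (day 2-14 mean 4.58): (6.745 + 12 × 4.58)/13 = 4.75 versus 4.58, +0.17.

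**Slower planning line.** Slope 2.34/14 = 0.167 per day. The inpatient mean is 8.50 - 0.0836L, so 1 versus 2 days gives 8.42 versus 8.33, +0.08. The home mean is the value at the midpoint of the phase: 7.25 versus 7.16, +0.08.

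**Rise to a peak, then fall to 3 at day 14.** With a peak at 24 hours, the 1-day inpatient mean is (6 + 8.50)/2 = 7.25. The fall is 5.5/13 = 0.423 per day, so day 1-2 averages 8.29 and the 2-day mean is 7.77.

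| Same curve in both arms, stay 1 vs 2 days | Inpatient difference | After-discharge difference |
|---|---|---|
| 8.50 to 6.16 by day 2, then flat | +0.59 | +0.05 |
| 8.50 to 6.16 by day 2, then to 4.93 at day 14 | +0.59 | +0.09 |
| 8.50 to 6.16 by day 2, then to 3 at day 14 | +0.59 | +0.17 |
| Straight line, 6.16 at day 14 | +0.08 | +0.08 |
| Peak at 24 h | -0.52 | +0.21 |
| Peak at 48 h | -0.63 | +0.16 |
| Peak at 72 h | -0.42 | +0.10 |

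Differences are the shorter-stay arm minus the longer-stay arm.

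**False-positive rates.** These come from 2,000 simulated trials with 46 per arm, between-patient SD 2.0, within-patient SD 1.0 (assumed), the curve falling to 3, and t-tests on patient phase means with no time term. Mean stays of 1 versus 2 days give 27% inpatient and 7% after discharge; with 34 per arm, 21% and 6%. For 1 versus 1.5 days (46 per arm) the rates are 11% and 6%. A rough check: SE = 2.0 × √(2/46) = 0.417 and 0.585/0.417 = 1.40, so about 29%. On the slower line, 0.084/0.417 = 0.20, so about 5.4%, barely above nominal.

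**With fixed windows.** A window set from surgery has the same mean whatever the stay. On the curve falling to 3, the 14-day mean is (2 × 7.33 + 12 × 4.58)/14 = 4.97, and split at day 1 it is (7.915 + 61.705)/14 = 4.97. In the 1 versus 2 day simulation, windows of 0-72 hours and after 72 hours give 4.8% and 5.1%, and the 14-day average gives 4.9%.

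**The case against.** The best defence has four parts.

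- **This is a supporting breakdown.** Aim 2 concerns cumulative pain, and the endpoint that answers it runs over a fixed 14 days. That stands. A reader might infer that the Aim 2 conclusion is compromised; the documents do not support this.
- **The direction is not established.** A reader might infer that a shorter stay makes an arm look worse in both phases. That needs pain to fall from the end of surgery onward. The 5.6.1 averages suggest it, but 5.6 expects a peak at 24-72 hours, and an initial rise reverses the inpatient sign. The scale matters too: on unnormalised totals, a 1-day instead of a 2-day stay simply moves 6.745 point-days from the inpatient phase to the home phase. This stands.
- **The model may handle time.** The planned analysis is a mixed model in a sentence about pain over time, and 5.6 allows covariates. A correct term for time since surgery would remove much of the timing bias, and the figures above are for unadjusted means. But no such term is specified for the phase comparison, and it would not undo the selection of who is still in hospital.
- **The split follows a real change in measurement.** Readings go from every 4 hours and on medication request to one evening score at least 2 hours after medication. This is a fair reason to describe inpatient pain separately. It does not justify a between-arm test within a phase whose length may depend on treatment.

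**Conclusion.** The point holds as a weakness of a supporting analysis. The phases are defined by a post-randomisation outcome, so any between-arm difference in LOS biases the phase comparison.

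The size is uncertain. For stays assumed to differ by a day, the inpatient bias runs from about -0.6 to +0.6 NPRS points depending on the early pain curve, and is only about +0.08 on the slower planning line. The after-discharge bias is small, roughly +0.05 to +0.2. All of this is conditional: the documents give no LOS and no expected difference in LOS, and nothing in them shows that RelieVRx shortens or lengthens the stay. If LOS is the same in both arms, the timing bias disappears. The sample size of 68 evaluable and 92 enrolled is untouched.

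**What to change.** In the secondary-endpoint paragraph of 5.6, define the phase comparison by windows counted from end of surgery and identical for every patient, wherever they are. The acute endpoint already supplies a set: 0-72 hours, the following week, and after day 10 to day 14. Within each window, use the time-weighted %AUC or include a model term for time since surgery, because the frequency of pain readings changes at discharge. Report inpatient-only pain descriptively, without a between-arm test. Settle this before any data are compared by arm.

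The cost is a sentence or two; the data and sample size are unchanged. There is a small downside: a fixed early window mixes inpatient and home readings taken under different rules, and the mix will still vary with LOS. That should be noted when the window is interpreted.
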